5.9.4. Overall Survival

Overall survival (OS) is defined as the time from the date of first dose until the date of death due to any cause. If the patient is alive at the cutoff date for the analysis (or was lost to follow-up without a confirmed date of death), OS will be censored on the last date the patient was known to be alive.

5.10. Subgroup Analyses

Subgroup analyses may be performed as deemed appropriate. The following analyses will be considered, depending on the number of patients within each subgroup:

- Safety analyses based on different infusion type of doxorubicin (intravenous route of administration over 60 minutes versus a 24-hour continuous infusion).
- Safety analyses related to cardiac toxicity based on subgroup of patients received dexrazoxane.
- Safety analyses related to urotoxicity based on different mesna dose levels.

5.11. Pharmacokinetics and Immunogenicity

A separate analysis plan will be provided for PK and immunogenicity analyses.

5.12. Biomarker Analysis

The detailed biomarker analysis will be included in a separate biomarker analysis plan.

5.13. Development Safety Update Report

The following reports are needed for the Development Safety Update Report (DSUR):

- Exposure information
- Listing of subjects who died during the DSUR period
- Discontinuations due to AEs during the DSUR Period

5.14. Clinical Trial Registry

Additional analyses will be performed for the purpose of fulfilling the Clinical Trial Registry (CTR) requirements. Analyses provided for the CTR requirements include the following:

- Summary of AEs, provided as a dataset which will be converted to an XML file. Both SAEs and “Other” AEs are summarized by treatment group and by MedDRA Preferred Term.
- An AE is considered “Serious” whether or not it is a TEAE.
- An AE is considered in the “Other” category if it is both a TEAE and is not serious.
- For each SAE and “Other” AE, for each term and treatment group, the following are provided:
 - the number of participants at risk of an event (if certain subjects cannot be at risk for some reason, for example, gender-specific AEs, then the number will be adjusted to only include the patients at risk)
 - the number of participants who experienced each event term
 - the number of events experienced.

- For each SAE, for each term and treatment group, the following are also provided for the EudraCT results submission:
 - The number of occurrences (events) causally related to treatment
 - The total number of deaths
 - The number of deaths causally related to treatment
- Consistent with www.ClinicalTrials.gov requirements, a threshold for frequency of “Other” AEs can be implemented rather than presenting all “Other” AEs. For example, “Other” AEs that occur in fewer than 5% of patients in any treatment group may not be included if a 5% threshold is chosen. The frequency threshold must be less than or equal to the allowed maximum of 5%.
- A participant flow will be created that will describe:
 - Number of participants per treatment arm. Screen failures do not need to be included. Number of participants who did not complete the study per treatment arm. This analysis will be based on study discontinuation, not treatment discontinuation.
 - Reasons participants did not complete the study.

6. References

7. Appendices

Appendix 1. List of Preferred Terms for AESI

AESI

Cardiac Dysfunction

Preferred Term

Acute left ventricular failure
Acute pulmonary oedema
Acute right ventricular failure
Cardiac asthma
Cardiac failure
Cardiac failure acute
Cardiac failure chronic
Cardiac failure congestive
Cardiac failure high output
Cardiogenic shock
Cardiopulmonary failure
Cardiorenal syndrome
Chronic left ventricular failure
Chronic right ventricular failure
Cor pulmonale
Cor pulmonale acute
Cor pulmonale chronic
Ejection fraction decreased
Hepatic congestion
Hepatojugular reflux
Left ventricular failure
Low cardiac output syndrome
Neonatal cardiac failure
Obstructive shock
Pulmonary oedema
Pulmonary oedema neonatal
Right ventricular failure
Ventricular failure
Artificial heart implant
Atrial natriuretic peptide abnormal
Atrial natriuretic peptide increased
Brain natriuretic peptide abnormal
Brain natriuretic peptide increased
Cardiac cirrhosis
Cardiac index decreased
Cardiac output decreased
Cardiac resynchronisation therapy
Cardiac ventriculogram abnormal
Cardiac ventriculogram left abnormal
Cardiac ventriculogram right abnormal
Cardiomegaly

AESI

Preferred Term

Cardio-respiratory distress
 Cardiothoracic ratio increased
 Central venous pressure increased
 Diastolic dysfunction
 Dilatation ventricular
 Dyspnoea paroxysmal nocturnal
 Heart transplant
 Hepatic vein dilatation
 Jugular vein distension
 Left ventricular dysfunction
 Myocardial depression
 Nocturnal dyspnoea
 N-terminal prohormone brain natriuretic peptide abnormal
 N-terminal prohormone brain natriuretic peptide increased
 Oedema
 Oedema due to cardiac disease
 Oedema neonatal
 Oedema peripheral
 Orthopnoea
 Peripheral oedema neonatal
 Pulmonary congestion
 Right ventricular dysfunction
 Scan myocardial perfusion abnormal
 Stroke volume decreased
 Systolic dysfunction
 Venous pressure increased
 Venous pressure jugular abnormal
 Venous pressure jugular increased
 Ventricular assist device insertion
 Ventricular dysfunction
 Ventricular dyssynchrony
 Chronotropic incompetence
 Electrocardiogram repolarisation abnormality
 Electrocardiogram RR interval prolonged
 Electrocardiogram U-wave abnormality
 Sudden cardiac death
 Bradycardia
 Cardiac arrest
 Cardiac death
 Cardiac telemetry abnormal
 Cardio-respiratory arrest
 Electrocardiogram abnormal
 Electrocardiogram ambulatory abnormal

Cardiac Arrhythmias

AESI

Preferred Term

Electrocardiogram change
Heart rate abnormal
Heart rate decreased
Heart rate increased
Loss of consciousness
Palpitations
Rebound tachycardia
Sudden death
Syncope
Tachycardia
Tachycardia paroxysmal
Bradycardia
Ventricular asystole
Accessory cardiac pathway
Adams-Stokes syndrome
Agonal rhythm
Atrial conduction time prolongation
Atrioventricular block
Atrioventricular block complete
Atrioventricular block first degree
Atrioventricular block second degree
Atrioventricular conduction time shortened
Atrioventricular dissociation
Bifascicular block
Brugada syndrome
Bundle branch block
Bundle branch block bilateral
Bundle branch block left
Bundle branch block right
Conduction disorder
Defect conduction intraventricular
Electrocardiogram delta waves abnormal
Electrocardiogram PQ interval prolonged
Electrocardiogram PQ interval shortened
Electrocardiogram PR prolongation
Electrocardiogram PR shortened
Electrocardiogram QRS complex prolonged
Electrocardiogram QT prolonged
Electrocardiogram repolarisation abnormality
Lenegre's disease
Long QT syndrome
Sinoatrial block
Trifascicular block
Ventricular dyssynchrony
Wolff-Parkinson-White syndrome

AESI

Preferred Term

Nodal arrhythmia
Nodal rhythm
Sick sinus syndrome
Sinus arrest
Sinus arrhythmia
Sinus bradycardia
Wandering pacemaker
Arrhythmia
Heart alternation
Heart rate irregular
Pacemaker generated arrhythmia
Pacemaker syndrome
Paroxysmal arrhythmia
Pulseless electrical activity
Reperfusion arrhythmia
Withdrawal arrhythmia
Arrhythmia supraventricular
Atrial fibrillation
Atrial flutter
Atrial parasystole
Atrial tachycardia
Junctional ectopic tachycardia
Sinus tachycardia
Supraventricular extrasystoles
Supraventricular tachyarrhythmia
Supraventricular tachycardia
ECG P wave inverted
Electrocardiogram P wave abnormal
Retrograde p-waves
Anomalous atrioventricular excitation
Cardiac flutter
Extrasystoles
Tachyarrhythmia
Accelerated idioventricular rhythm
Cardiac fibrillation
Parasystole
Rhythm idioventricular
Torsade de pointes
Ventricular arrhythmia
Ventricular extrasystoles
Ventricular fibrillation
Ventricular flutter
Ventricular parasystole
Ventricular pre-excitation
Ventricular tachyarrhythmia

AESI

Encephalopathy

Preferred Term

Ventricular tachycardia

Blurred vision

Coma

Confusion

Extrapyramidal symptoms

Hallucinations

Psychotic behavior

Seizures

Somnolence

Urinary incontinence

Infusion-related Reactions

Allergic oedema

Anaphylactic reaction

Anaphylactic shock

Anaphylactoid reaction

Anaphylactoid shock

Angioedema

Circulatory collapse

Circumoral oedema

Conjunctival oedema

Corneal oedema

Cytokine release syndrome

Dialysis membrane reaction

Distributive shock

Drug hypersensitivity

Epiglottic oedema

Eye oedema

Eye swelling

Eyelid oedema

Face oedema

Gingival oedema

Gingival swelling

Gleich's syndrome

Hypersensitivity

Idiopathic urticaria

Infusion related reaction

Kounis syndrome

Laryngeal oedema

Laryngotracheal oedema

Limbal swelling

Lip oedema

Lip swelling

Oculorespiratory syndrome

Oedema mouth

Oropharyngeal swelling

Palatal oedema

AESI**Preferred Term**

	Periorbital oedema
	Pharyngeal oedema
	Scleral oedema
	Shock
	Swelling face
	Swollen tongue
	Tongue oedema
	Tracheal oedema
	Type 1 hypersensitivity
	Urticaria
	Urticaria cholinergic
	Urticaria chronic
	Urticaria popular
Renal toxicity: Nephrotoxicity	Acute renal failure
	Aminoaciduria
	Chronic renal failure
	Cylindruria
	Decrease in glomerular filtration rate
	Enzymuria
	Fanconi syndrome
	Glycosuria
	Increased serum creatinine
	Phosphaturia
	Proteinuria
	Renal dysfunction
	Tubular acidosis
	Tubulointerstitial nephritis
Renal toxicity: Urotoxicity	Hemorrhagic cystitis
	Hematuria
	RBC in urine

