7.1.3. Ifosfamide Premedications and Mesna Administration

Mesna must be administered to all patients for the prevention of ifosfamide-induced hemorrhagic cystitis. Mesna should be administered at a minimum dose equal to 60% of the ifosfamide dose according to institutional guidelines. Note that as the dose of mesna administered is dependent on the dose of ifosfamide administered, any dose modifications to ifosfamide will require a corresponding dose modification to mesna in order to maintain the correct dosage (mesna dose = minimum 60% of ifosfamide dose).

Ifosfamide should be given with extensive hydration consisting of oral or IV fluid (≥ 2 L/m² per day IV) to prevent bladder toxicity or according to institutional guidelines.

Ifosfamide is associated with moderate emetic potential and antiemetics are recommended to prevent nausea or vomiting.

If ifosfamide premedication is required, it should be administered together with any doxorubicin premedications prior to doxorubicin administration.

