7.4.3.2.3. Monitoring for Doxorubicin-Associated Cardiotoxicity

Cardiotoxicity is a recognized risk of doxorubicin that increases with higher cumulative drug exposure. Cardiac monitoring is conducted by a combination of monitoring of clinical parameters, ECG, and echocardiogram (ECHO)/multiple-gated acquisition (MUGA) scan.

Changes in ECG, arrhythmias, tachycardia and/or chest pain should be managed based on the specific findings.

Patients will undergo baseline LVEF determination using ECHO or MUGA scan. This evaluation may be repeated at any time during the study if clinically indicated. A decrease in LVEF of \geq 10% and below the lower limit of normal, or an absolute decrease of 20%, or if the absolute LVEF decreases to or below 40%, then doxorubicin will be discontinued. Doxorubicin should also be discontinued if the patient develops Grade 3 or 4 left ventricular systolic dysfunction (symptomatic congestive heart failure).

The diagnostic method used at baseline for cardiovascular assessments (for example, ECHO or MUGA scans) should be the same method used throughout the study, unless there is clinical or instrumental evidence that further investigations are needed.

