5.8.3. Adverse Events

Adverse event (AE) severity grades will be assigned by the investigator using Common Terminology Criteria for Adverse Events (CTCAE) Version 4. AE verbatim text will be mapped by the sponsor or designee to corresponding terminology within MedDRA.

Pre-existing conditions are defined as any AEs that begin prior to the first dose of study drug.

Treatment-emergent adverse event (TEAE) are defined as any AE that occurred or worsened between the day of first dose and up to 30-day follow-up visit (or up to any time if serious and related to study treatment).

Comparisons of pre-existing conditions to on-treatment events at the low level term (LLT) level will be used in the treatment-emergent computation.

The following AE will be considered as **AE of special interest (AESI)** for the combination of olaratumab and doxorubicin, ifosfamide and mesna: infusion-related reactions (IRR), cardiac arrhythmias, cardiac dysfunction, encephalopathy, renal toxicity. PT for AESI are listed in [Appendix 1](#). Categories of AESI may be modified as the understanding of the safety of the investigational drug increases. The final list of categories will be reported in the clinical study report (CSR).

Consolidated AE will include Abdominal Pain, Anemia, Fatigue, Hyperbilirubinaemia, Hypertension, Hypoalbuminaemia, Hypokalaemia, Hypomagnesaemia, Hyponatraemia, Hypoproteinemia, Intestinal Obstruction, Leukocytosis, Leukopenia, Lymphopenia, Mucositis, Neuropathy, neutropenia, Musculoskeletal pain, Rash, and Thrombocytopenia. Each consolidated AE contains PTs identified as clinically identical or synonymous. PT for consolidated AEs are listed in [Appendix 2](#).

The following summaries and listings will be produced:

- Overview of AE
- Summary of TEAE by PT (any grade and Grade ≥ 3)
- Summary of DLT
- Summary of DET
- Summary of TEAE by system organ class (SOC) and PT (any grade and Grade ≥ 3)
- Summary of TEAE by SOC and PT and maximum grade (1-5)
- Summary of treatment-emergent serious AE (SAE) by SOC and PT (any grade and Grade ≥ 3)
- Summary of AEs as reason for study treatment discontinuation by SOC and PT
- Summary of and listing of TEAE leading to dose delays, omissions, interruptions, reductions, treatment discontinuation, hospitalizations, transfusions

- Summary of treatment-emergent AESI (any grade and Grade ≥ 3)
- Summary of treatment-emergent consolidated AE (any grade and Grade ≥ 3)
- Listings of DLT, DET, SAE, TEAE, AESI

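### The Cardiac Dysfunction AESI list pools non-specific oedema and sign terms with specific cardiac terms in one count and has no cardiomyopathy or cardiotoxicity term, so its any-grade rate is hard to interpret

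*SAP*

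**What the plan says.** Protocol 9.2.3 makes cardiac arrhythmias and cardiac dysfunction an adverse event of special interest and says that each AESI is built by grouping related MedDRA preferred terms. SAP Appendix 1 gives the grouping. Under Cardiac Dysfunction it includes direct terms such as "Ejection fraction decreased" and "Left ventricular dysfunction", and several cardiac-failure terms. The same list holds plain Oedema and "Oedema peripheral", neither limited to a cardiac cause, although "Oedema due to cardiac disease" is listed separately. It also holds nocturnal dyspnoea, hepatic congestion and abnormal or raised natriuretic peptides.

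SAP 5.8.3 lists the output as "Summary of treatment-emergent AESI (any grade and Grade" 3 or higher. It states no specific/broad split and no case review.

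Protocol 7.4.3.2.3 says: "Cardiotoxicity is a recognized risk of doxorubicin that increases with higher cumulative drug exposure". Protocol 7.1.3 says: "Ifosfamide should be given with extensive hydration consisting of oral or IV fluid". SAP 5.8.8 summarises LVEF by time point and the percentage of patients who meet LVEF-decrease criteria.

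**The concern.** An AESI count is usually read as the number of patients who had the named problem. Here a patient with ankle swelling and a patient in heart failure add the same amount to the any-grade figure. Characterising safety is part of the primary objective, and doxorubicin's effect on the heart is a known risk of the backbone. The study is nonrandomised and each cohort is single-arm, so no comparator shows how much oedema would occur anyway.

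The regimen has a plausible non-cardiac source of swelling in the fluid given with ifosfamide. That is an inference: Protocol 7.1.3 mentions hydration only as protection for the bladder.

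The list may also be too narrow in one place. The protocol calls the doxorubicin risk cardiotoxicity, but Appendix 1 has no term with that word and none for cardiomyopathy. SAP 5.10 also considers cardiac-toxicity analyses in patients given dexrazoxane, without naming the measure. If the AESI is used there, it would carry the same lack of specificity.

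**Working it through.** The plan states no expected rate of oedema or cardiac dysfunction, so there is no figure to reproduce.

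**Step 1: contents of the list.** The Cardiac Arrhythmias label is out of line in the text available, so I took the arrhythmia block to begin at Chronotropic incompetence. That leaves 72 Cardiac Dysfunction terms; the oedema terms come earlier and are unaffected.

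- Containing cardiotox- or cardiomyop-: 0 of 72, and none in the rest of Appendix 1. The nearest are "Myocardial depression", Cardiomegaly and Dilatation ventricular.
- Containing oedema: 8. The two with no qualifier of cause or age are Oedema (no site either) and "Oedema peripheral".
- Containing failure: 14. Containing dysfunction: 5. Ejection fraction: 1.
- Neonatal terms: 4, although Inclusion Criterion 3 requires age 18 or over.
- Order: 28 mostly heart-failure terms in alphabetical order, then the alphabet restarts with 44 further terms, among them both unqualified oedema terms. 28 + 44 = 72.

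A rough tiering is thus already visible, but the SAP does not use it. Some specific terms, such as Left ventricular dysfunction and Systolic dysfunction, sit in the second block.

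**Step 2: match with the protocol's cardiac event.** Protocol 7.4.3.2.3 stops doxorubicin for stated LVEF falls or for Grade 3–4 left ventricular systolic dysfunction. The list covers these with ejection-fraction, ventricular-dysfunction and cardiac-failure terms. The gap concerns only events coded solely to an absent term.

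**Step 3: illustration of dilution.** Inputs:

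- c = true cardiac dysfunction rate, assumed 2–10%
- o = non-cardiac oedema rate, assumed 2–30%
- the two independent, and every true event captured by a listed term
- about 30 patients on the recommended regimen (Protocol 5.2)

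Formulas:

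- AESI rate a = 1 − (1 − c)(1 − o)
- oedema-only share = (a − c)/a

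Example with c = 5%, o = 20%: a = 1 − 0.95 × 0.80 = 24.0%; share = (0.24 − 0.05)/0.24 = 79%. In 30 patients that is 7.2 counted, of whom 1.5 have true events.

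| c | o = 2% | o = 5% | o = 10% | o = 20% | o = 30% |
|---|---|---|---|---|---|
| 2% | 4.0% (49%) | 6.9% (71%) | 11.8% (83%) | 21.6% (91%) | 31.4% (94%) |
| 5% | 6.9% (28%) | 9.8% (49%) | 14.5% (66%) | 24.0% (79%) | 33.5% (85%) |
| 10% | 11.8% (15%) | 14.5% (31%) | 19.0% (47%) | 28.0% (64%) | 37.0% (73%) |

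Each cell gives the AESI rate, with the oedema-only share in brackets. Without the unqualified oedema terms the rate would be c, or 0.6 to 3 of 30 patients.

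**Step 4: when oedema dominates.** The share exceeds one half when o(1 − c) > c, that is o > c/(1 − c). For c = 2%, 5% and 10% the thresholds are 2.04%, 5.26% and 11.1%. Oedema therefore dominates once it is slightly commoner than true dysfunction, and not otherwise.

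**The case against.** A broad, sensitive list is a legitimate choice in a small descriptive safety study, and several planned outputs limit the harm.

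- **LVEF.** SAP 5.8.8 reports the same three LVEF thresholds that stop doxorubicin in Protocol 7.4.3.2.3, whatever the AE coding. This is a strong safeguard, but the SAP does not link it to the AESI, and routine on-treatment scans come only at the end of Cycles 4 and 6.
- **By-term tables and listings.** SAP 5.8.3 tabulates TEAEs by preferred term, so a reader can see oedema and cardiac failure separately. But a patient may have several terms, and adding the rows does not give a count of patients with any specific cardiac event.
- **Grade 3 or higher.** This line should remove much of the mild oedema, but it also removes lower-grade cardiac events.
- **Treatment-emergent rule.** Oedema present at baseline counts only if it worsens, so swelling from a limb tumour is partly handled.
- **Decisions.** Cohort progression rests on DLT counts, with later safety data considered. No rule uses the AESI percentage.
- **Flexibility.** SAP 5.8.3 lets AESI categories be modified. Changing the terms after open-label data have been seen is weaker than fixing them in advance.

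Two stronger readings are tempting. A reader might infer that oedema will swamp the rate. For instance, assuming 3–5% true dysfunction, 15–25% oedema and no overlap in 30 patients gives (1.5 + 4.5)/1.5 = 4.0-fold to (0.9 + 7.5)/0.9 = 9.3-fold inflation. The documents supply none of those rates, and other assumed values in the table leave oedema in the minority.

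A reader might also infer that the AESI misses doxorubicin cardiotoxicity altogether. Step 2 shows that it does not. How a report worded as cardiotoxicity would be coded depends on MedDRA, which the documents do not reproduce.

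**Conclusion.** The concern holds in a limited form. The list pools specific and non-specific terms in one count and omits cardiomyopathy and cardiotoxicity terms, and no planned table gives a de-duplicated count of patients with specific cardiac events. In a study without a control arm, the any-grade rate is therefore non-specific and can be mostly oedema.

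The range of 15% to 94% rests entirely on assumed rates and independence. It shows how far the figure could vary and does not forecast it. If oedema and cardiac events tend to occur in the same patients, the oedema-only share falls; if the other non-specific terms are included, the non-specific share rises. The omission matters only for an event coded solely to an absent term. The effect is on how the safety results are read; dose-finding rules are untouched.

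**What to change.** In SAP Appendix 1, split Cardiac Dysfunction into two tiers and carry both into the AESI summary of SAP 5.8.3:

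1. A specific line as the main result, counting each patient once: heart-failure, ventricular-dysfunction and ejection-fraction terms, plus the cardiomyopathy and cardiotoxicity terms of the MedDRA version in use.
2. A broad supportive line using the full list, including the oedema, congestion, dyspnoea and marker terms.

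Show the specific line at any grade and at Grade 3 or higher, beside the percentage of patients meeting the LVEF-decrease criteria of SAP 5.8.8. Set the tiers before the data are reviewed.

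The cost is re-sorting one appendix, adding a few terms and printing one extra table line. No new data are needed, and the sensitive list is kept.

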7.4.3.3. Ifosfamide Toxicities and Dose Modifications

Dose modifications of ifosfamide will follow the guidelines outlined below and may be adjusted according to local standard of care and label. Two reductions in ifosfamide dose for toxicity will be permitted during the study. If a third dose reduction is necessary, the patient will be discontinued from the combination therapy (olaratumab + doxorubicin/ifosfamide/mesna) and followed as outlined in Section 7.4.2.

General guidelines for ifosfamide dose modification are shown in Table JGDR.12. Dose modifications of ifosfamide due to hepatic impairment are shown in Table JGDR.13.

Table JGDR.12. General Guidelines for Dose Modification of Ifosfamide due to Toxicity

Worst Toxicity/Counts in Previous Cycle	Ifosfamide Dose Reduction ^a
Febrile neutropenia	First episode: Maintain full dose Subsequent episodes: Decrease 20%
Platelets <75,000/mm ³	If less than 1 week duration: Maintain full dose If greater than 1 week duration: Decrease 20%
Thrombocytopenic bleeding	Decrease 20%
Somnolence or other signs of encephalopathy	Discontinue combination therapy (olaratumab + doxorubicin/ifosfamide/mesna) and follow per Section 7.4.2. Administer methylene blue 50 mg intravenously every 4 hours until resolution.
Grade 3 or 4 neurotoxicity other than encephalopathy	Discontinue combination therapy (olaratumab + doxorubicin/ifosfamide/mesna) and follow per Section 7.4.2.
Grade 3 related organ toxicity/nonhematologic	Decrease 20%
Grade 4 related organ toxicity/nonhematologic	Discontinue combination therapy (olaratumab + doxorubicin/ifosfamide/mesna) and follow per Section 7.4.2.

Abbreviation: mg = milligrams.

^a Do not re-treat until criteria in Section 7.4 are met.

Table JGDR.13. Dose Modification of Ifosfamide due to Hepatic Impairment

Bilirubin	and/or	AST/ALT	Ifosfamide Dose Reduction ^a
1-2 × ULN		<2 × ULN	Full dose
2-4 × ULN		2-5 × ULN	75% of initial dose
>4 × ULN		>5 ULN	Discontinue combination therapy (olaratumab + doxorubicin/ifosfamide/mesna) and follow per Section 7.4.2.

Abbreviations: ALT = alanine aminotransferase; AST = aspartate aminotransferase; ULN = upper limit of normal.

^a Based on clinical judgment – less conservative adjustments can be considered if hepatic changes are secondary to metastases rather than hepatic cirrhosis or hepatitis.

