7.4.3.3.1. Ifosfamide-Associated Central Nervous System Toxicity

Central nervous system toxicity appears to be dose dependent, and is variable in onset, but usually resolves when ifosfamide is discontinued. Incidence is higher with higher doses, concomitant use of aprepitant, electrolyte imbalances, renal/hepatic impairment, or preexisting CNS disorders. It may manifest as transient mental status changes (somnolence, confusion, hallucination, disorientation and lethargy), cerebellar dysfunction, extrapyramidal symptoms, transient weakness, cranial nerve dysfunction, or seizure activity. Methylene blue, which may act as an electron acceptor or decrease chloroacetaldehyde formation, has been suggested as treatment or prophylaxis for ifosfamide-induced encephalopathy. Due to the potential for additive effects, drugs acting on the CNS (such as antiemetics, sedatives, narcotics, or antihistamines) must be used with particular caution or, if necessary, be discontinued in case of ifosfamide-induced encephalopathy.

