9.2.3. Adverse Events of Special Interest

Adverse events of special interest (AESI) are events that have been identified as safety signals during preclinical or early clinical trials or based on class effects of similar drugs. These events will be monitored prospectively in the clinical developmental program. Each event is defined by a careful assessment and grouping of individual related Medical Dictionary for Regulatory Activities (MedDRA) preferred terms.

The following events will be considered as AESI for the combination of olaratumab and doxorubicin, ifosfamide and mesna:

- infusion-related reactions
- cardiac arrhythmias and cardiac dysfunction
- encephalopathy
- renal toxicity

Refer to Section 7.8.1 for treatment considerations relative to the occurrence of olaratumab IRRs. Refer to Section 7.4 for treatment considerations relative to dose delays, modifications and discontinuations from doxorubicin, including AEs of concern or AESI.

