Appendix 2. List of Preferred Terms for Consolidated AE

Consolidated AE	Preferred Term
Abdominal pain	Abdominal pain Abdominal pain lower Abdominal pain upper
Anaemia	Anaemia Haemoglobin decreased Red blood cell count decrease
Fatigue	Asthenia Fatigue
Hyperbilirubinaemia	Blood bilirubin increased Hyperbilirubinaemia
Hypertension	Hypertension Blood pressure increased
Hypoalbuminaemia	Blood albumin decreased Hypoalbuminaemia
Hypokalaemia	Blood potassium decreased Hypokalaemia
Hypomagnesaemia	Blood magnesium decreased Hypomagnesaemia Magnesium deficiency
Hyponatraemia	Blood sodium decreased Hyponatraemia
Hypoproteinemia	Hypoproteinemia Protein total decreased
Intestinal obstruction	Gastrointestinal obstruction Intestinal obstruction Small intestinal obstruction
Leukocytosis	Leukocytosis White blood cell count increased
Leukopenia	Leukopenia White blood cell count decreased
Lymphopenia	Lymphocyte count decreased Lymphopenia
Mucositis	Aphthous stomatitis Mucosal inflammation Oropharyngeal pain Stomatitis
Musculoskeletal pain	Arthralgia Back Pain Bone Pain Flank Pain Groin Pain

Consolidated AE	Preferred Term
	Muscle Spasms
	Musculoskeletal Chest Pain
	Musculoskeletal Pain
	Myalgia
	Neck Pain
	Pain In Extremity
Neuropathy	Hypoaesthesia
	Neuropathy peripheral
	Paraesthesia
	Peripheral sensory neuropathy
Neutropenia	Neutropenia
	Neutrophil count decreased
Rash	Dermatitis
	Dermatitis acneiform
	Dermatitis allergic
	Dermatitis bullous
	Rash
	Rash follicular
	Rash generalised
	Rash macular
	Rash papular
	Rash pruritic
	Rash pustular
Thrombocytopenia	Platelet count decreased
	Thrombocytopenia

Leo Document ID = bcc6fdde-8d46-4c69-a893-34d6098e01e9

Approver: PPD

Approval Date & Time: 28-Aug-2017 12:24:08 GMT

Signature meaning: Approved

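### The SAP's term list for the Encephalopathy AESI does not contain Encephalopathy, so an event coded under that name would miss its own AESI row

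*SAP*

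**What the plan says.** Protocol 9.2.3 includes encephalopathy and renal toxicity among the AESIs and states how an AESI is built: "Each event is defined by a careful assessment and grouping of individual related Medical Dictionary for Regulatory Activities (MedDRA) preferred terms". SAP 5.8.3 gives the categories as "infusion-related reactions (IRR), cardiac arrhythmias, cardiac dysfunction, encephalopathy, renal toxicity". For their content it adds "PT for AESI are listed in" Appendix 1. It then plans a treatment-emergent AESI summary (any grade and Grade 3 or higher) and an AESI listing.

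Under the Encephalopathy label, Appendix 1 gives nine terms, of which "Psychotic behavior" is one. The label is not repeated as a term.

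The protocol describes ifosfamide CNS toxicity in 7.4.3.3.1 as possibly showing itself through "transient mental status changes (somnolence, confusion, hallucination, disorientation and lethargy), cerebellar dysfunction, extrapyramidal symptoms", and also through transient weakness, cranial nerve dysfunction or seizures. Table JGDR.12 has a row for "Somnolence or other signs of encephalopathy" and a separate row for Grade 3 or 4 neurotoxicity other than encephalopathy.

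SAP 5.8.3 also allows the AESI categories to be modified as knowledge of the drug's safety grows, with the final list of categories reported in the clinical study report.

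**The concern.** The term list decides who is counted. If it leaves out the most direct name for the event, the row can miss exactly the patients it is meant to show. The protocol itself uses the word encephalopathy in 7.4.3.3.1, in 9.2.3 and in Table JGDR.12, so an investigator could readily report the event in that word.

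An AESI table exists to gather related terms that tables by system organ class and preferred term scatter. A reader who wants the encephalopathy rate for this combination will go to that row first and has no reason to suspect that Encephalopathy is excluded from it.

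**Working it through.** The plan states no figure on this point, so the check is a comparison of lists.

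**1. Is the naming term in the list?** None of the nine entries is Encephalopathy. This does not look like text lost in extraction, because the list is alphabetical and shows no gap where the term would sit. Other categories do contain their naming term: the infusion reaction list includes Infusion related reaction, and the arrhythmia list includes Arrhythmia.

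**2. How does the list compare with the protocol's CNS signs?** Protocol 7.4.3.3.1 names ten.

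| Protocol 7.4.3.3.1 sign | Counterpart in SAP Appendix 1, Encephalopathy |
|---|---|
| Somnolence | yes |
| Confusion | yes |
| Hallucination | yes |
| Disorientation | no |
| Lethargy | no |
| Cerebellar dysfunction | no |
| Extrapyramidal symptoms | yes |
| Transient weakness | no |
| Cranial nerve dysfunction | no |
| Seizure activity | yes |

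Five of ten have a counterpart. Of the five mental status changes (the first five rows), three are listed and two are not. The other four SAP terms (9 − 5 = 4) are coma, psychotic behavior, blurred vision and urinary incontinence, which that protocol paragraph does not name.

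**3. Are the entries written as dictionary terms?** The urotoxicity block has "Hemorrhagic cystitis" and the nephrotoxicity block has Increased serum creatinine: American spelling, and the modifier first. Appendix 2 has "Haemoglobin decreased" and Blood bilirubin increased: British spelling, and the direction last. The cardiac list follows the second pattern, for example Ejection fraction decreased. The encephalopathy list also uses American spelling, in "Psychotic behavior". All of these stand under the heading Preferred Term. Some entries may therefore not be verbatim dictionary terms.

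**4. What does one missed patient do to the rate?** SAP 5.8 reports safety within each cohort and also pools the confirmation phase with the same dose level from the dose-finding phase. One patient is 1/15 = 6.7 percentage points in a cohort of 15, and 1/30 = 3.3 points in the pooled group of about 30. How many patients would be missed cannot be derived from the documents.

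**The case against.** **The events are not lost.** An event coded Encephalopathy still appears in the treatment-emergent tables by preferred term, by system organ class and by maximum grade, in the repeats for related events, and in the serious event tables if it is serious. A related nonhematologic event of Grade 3 or higher in Cycle 1 can be a DLT whether or not it is an AESI. This stands. A reader might infer that the primary safety profile would be understated, but the documents support a defect only in the AESI summary and listing.

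**The direction of the net error is open.** Blurred vision and urinary incontinence are non-specific and could bring in unrelated patients. A patient coded Encephalopathy who also has a listed sign, such as somnolence or coma, is still counted. This stands too, and is why the point is limited to a patient with no listed term.

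**Not every sign in 7.4.3.3.1 belongs in the list.** That paragraph covers CNS toxicity in general, and Table JGDR.12 separates encephalopathy from other neurotoxicity. Adding cerebellar or cranial nerve dysfunction could merge groups that the protocol keeps apart. This is right. The case is stronger for disorientation and lethargy, because the protocol groups them with somnolence and confusion, which are listed.

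**Spelling proves nothing about counts.** A reader might infer that renal toxicity would be under-counted as well. That would need the MedDRA term list and the matching rule, and the documents give neither. If a reviewer maps the terms, the effect could be nil. Nor is the contrast clean: Appendix 2 has Hypoproteinemia beside Hypoalbuminaemia, and SAP 5.8.3 writes Anemia where Appendix 2 writes Anaemia. The mixed style justifies a dictionary check and no more.

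**The SAP expects revision.** Its clause covers the categories. It does not provide for checking the terms inside one, so it does not repair this list.

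**Conclusion.** The point holds for encephalopathy and is wrong as written. Applied literally, Appendix 1 leaves a patient whose only relevant event is coded Encephalopathy out of the Encephalopathy AESI row and listing. Two mental status terms named by the protocol are missing as well. Whether they belong is a judgement that the SAP should record.

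The conclusion assumes that the AESI outputs are programmed from Appendix 1, as SAP 5.8.3 indicates, and that events can be coded to Encephalopathy in the dictionary used. The dictionary check in the fix would settle the second assumption. The defect is small in scope and its numerical size is unknown. For renal toxicity, the documents support verifying the terms but do not show a wrong count.

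**What to change.** Before database lock, revise SAP Appendix 1 as follows:

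- Add Encephalopathy to the Encephalopathy list.
- Add disorientation and lethargy, or state why they are left out. Keep the distinction in Table JGDR.12 between encephalopathy and other neurotoxicity.
- Verify every entry in the encephalopathy, nephrotoxicity and urotoxicity lists against the MedDRA version in use, and replace any that is not a verbatim preferred term.
- State how coded events are matched to the lists.

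The cost is an appendix edit and a coding check, with no new data and no change to study conduct. Making the change early also matters because the study is open-label, and a list repaired after the events have been seen would be open to the charge of being post hoc.
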